#### 7 DATA ANALYSIS

Data management and statistical analyses will be performed in the Department of Health Sciences, University of Leicester.

#### 7.1 Expected number of cases

No studies of the occurrence of influenza, RSV, and *S. pneumoniae* infections in elderly and other high-risk adults presenting to Medical Admission Units with cardio-pulmonary conditions that employ sensitive diagnostics have been carried out. Indeed, it is the uncertainty of their burden – together with questions concerning the clinical and cost-effectiveness of rapid diagnostic tests for these infections that has prompted the proposed study.

We plan to carry out the study in the Medical Admission Units/medical wards of the three acute hospitals in Leicester, which provide acute medical care for approximately 1 million people of all ages. Of these,  $\sim 14\%$  (i.e., 140 000) are  $\geq 65$  years of age.

On the basis of medical admission data for the period September 1 – 30 April, 2002/3 and 2003/4, (when there were 2762 cardiopulmonary admissions during 242 days and 2852 during 243 days respectively), we anticipate that the acute hospitals will receive a daily average of 11.6 cardiopulmonary admissions  $\geq$ 65 years of age, excluding admissions for angina and myocardial infarction. The study will run **for 43** weeks each season during the winters 2005/6 and 2006/7, and for 26 weeks during the period 1st September 2007 to 1st March 2008, i.e over 242 days during the 2005/6 and 2006/7 winters, and for 182 days during winter 2007/8 (September 1 – March 1). During this period, we estimate that 7706 cardiopulmonary admissions aged  $\geq$ 65 years will be eligible for the proposed study. [Note: should there be a delay in starting the project we will recruit patients for 34 weeks during 'winter' 2007/8].

We will recruit patients five days per week. Thus, during the period Monday through Friday, the pool of eligible elderly ( $\geq 65$  years) patients that could be recruited will be 5504 (5/7 x 7706). We understand that

two-thirds are admitted during the period 09:00-21:00h, which reduces the pool of eligible subjects to 3669 (2/3 x 5504). We estimate that three-quarters of those who are invited to participate will do so (we carried out a study of respiratory virus infections in children at the Leicester Royal Infirmary; the parents of 86% agreed to participate). On the basis of these observations, we estimate that 2752 (3/4 x 3669) eligible elderly people could be recruited. Thus we anticipate recruiting a similar number of elderly patients as in the study by Falsey *et al*, which was carried out in Rochester and Syracuse hospitals over three winters.

On the basis of pneumonia admissions data for the elderly ( $\geq 65$  years) for the period September 1 – 30 April, 2002/3 and 2003/4 (when 1354 case were admitted over 485 days), we expect that 664 of an expected 1859 pneumonia (J12.9-J18.9) admissions will be recruited. Similarly we expect to recruit 556 participants with unspecified acute lower respiratory tract infections (J22.X), 683 with chronic obstructive pulmonary disease, and 735 participants with 'heart failure'.

The number of high-risk patients aged 18-64 years has not been factored into the above estimates. We have not been able to obtain historical data on the number of admissions among 18-64-year-olds to UHL hospitals who have underlying 'high-risk' medical conditions. However, by examining recent national data for admissions for comparable age groups, and making assumptions about the proportion of patients who have underlying high-risk conditions, we estimate that an additional 83 cases of pneumonia, 93 cases of unspecified acute lower respiratory tract infections, and 181 cases of COPD could be recruited.

- Based on the above, we expect to recruit 747 participants with pneumonia, of whom at least one third (n=249) should have *S. pneumoniae* infection. Of these, ~83 should be randomly allocated to the rapid near patient test (Binax NOW); the remainder will be randomised to the group tested by traditional methods. Thus the speed of diagnosis, impact of early diagnosis on prescribing, clinical outcomes, and costs will be assessed in groups having an estimated 83 and 166 subjects. However, as identical sample sets will be taken from each participant, the diagnostic accuracy of the tests will be assessed in all 249 subjects. The number of cases of *S. pneumonaie* infection that are likely to be identified among the anticipated 649 (556 +93) participants with unspecified acute lower respiratory tract infections is unknown, but their occurrence will add to the pool of cases for studies of diagnostic accuracy.
- On the basis of the Rochester study, we expect that 10% of the 2752 elderly (≥65 years) participants will have influenza A or B. Of the 275, one third (~92) will be allocated to the QuickView near patient influenza immunoassay; one third will be allocated to the rapid molecular group; the remainder will be allocated to the group tested by traditional methods. Identical sample sets will be taken from each individual, so the diagnostic accuracy of the tests will be assessed in all 275 subjects.
- Similarly, we expect that 5% of the 2752 elderly (≥65 years) participants will have RSV A or B. Of the 138, one third (~46) will be allocated to the rapid molecular group; the remainder (~92) will be allocated to the group tested by traditional methods. We expect that very few of these will be found

positive by the routine tests employed. Identical sample sets will be taken from each individual, so the diagnostic accuracy of the tests will be assessed in all 138 subjects.

While the numbers of patients with influenza and RSV who are allocated to the 'rapid' near patient or molecular tests are comparatively small (~92 + ~46 per elderly group, plus cases occurring in the 18-64-year-olds), the impact of a 'viral' infection (RSV or influenza) infection on patient isolation, antimicrobial prescribing, and clinical outcomes may be compared using a larger combined group – i.e.,

Elderly

Rapid influenza & RSV (i.e., Quickview + molecular tests) n=(92+92+46)=230Traditional influenza & RSV n=(92+46+46)=184

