	We expect that 10% of the 2752 (elderly) patients will have influenza A or B. Of the 275, one third (~91) will be allocated to Groups 1, 2, and 3. Identical sample sets will be taken from each individual, so the diagnostic accuracy of the tests will be assessed in all 275 subjects.
	We expect that 5% of the 2752 (elderly) patients will have RSV A or B. Of the 137, one third (~45) will be allocated to the rapid molecular group (Group 2); the remainder (~90) will be allocated to the groups tested by traditional methods (Group 1 & 3). Identical sample sets will be taken from each individual, so the diagnostic accuracy of the tests will be assessed in all 137 subjects.
	While the numbers of patients with influenza and RSV who are allocated to the 'rapid' near patient or molecular tests are comparatively small, the impact of a 'viral' infection (RSV or influenza) infection on patient isolation, antimicrobial prescribing, and clinical outcomes may be compared using larger combined groups – i.e., Rapid influenza & RSV (i.e., Quickview + molecular tests) $n = (91 + 91 + 45) = 227$ Traditional influenza & RSV $n = (91 + 45 + 45) = 182$ .
Statistical power:	This has been estimated for one laboratory and two clinical endpoints for the elderly population only.
	Diagnostic accuracy Assuming that the average sensitivity/specificity of the tests is $80\%[90\%]$ then allowing for a 20% dropout rate, a sample of 2752 (2000) i.e. only 2 winters) elderly ( $\geq$ 65 years) patients randomised into the trial would enable the sensitivity/specificity to be estimated to within, i.e. 2SE, 7.6% (8.9%) [5.7% (6.7%)] for a disease prevalence of 10%, and 5.4% (6.3%) [4.0% (4.7%)] for a disease prevalence of 5%.
	Length of Stay 2752 patients would enable a Minimum Clinically Significant Difference (MCSD) [between diagnostic policies] of 1 day in the mean length of stay (assuming SD=6 days) to be detected at the 5% significance level with over 80% power, assuming a 20% dropout rate and adjusting for the fact that there are 3 groups.
	Appropriate Isolation Levels: 2752 patients would also enable a Minimum Clinically Significant Difference (MCSD) [between diagnostic policies] of an improvement in appropriate use of isolation facilities from 5% to 15% to be detected at the 1% significance level with over 95% power, assuming a 20% dropout rate and adjusting for the fact that there are 3 groups.

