#### 1.2 Acute respiratory illnesses

Illness surveys conducted in general practice indicate an overwhelming importance of acute respiratory illness in comparison to other conditions. During the most recent National Morbidity Study, a higher proportion of people (31%) consulted for respiratory conditions at least once during the year than for diseases in any other single ICD chapter. Overall, 67% of patients who saw their GP with a respiratory condition did so because of an acute infection, i.e., ~20% of all consultations in primary care occur because of acute respiratory infections, which are mostly viral. A similar picture has emerged in the United States. Some important age differences have emerged. There is a very high incidence of 'colds' and lower respiratory illness in the very young, whereas in the elderly, there is an age-related increase in morbidity and mortality from 'pneumonia and influenza.' We propose in this study to evaluate rapid diagnostic technologies for three target pathogens, influenza, respiratory syncytial virus, and *S. pneumoniae*, which are key aetiological agents of acute respiratory illness, and collectively are responsible for considerable morbidity and mortality in the elderly.

There have been no studies of the comparative incidence of influenza, RSV and pneumococcal disease among elderly cardiopulmonary admissions. Falsey *et al* evaluated the number of hospitalisations of RSV infection relative to influenza in several thousand elderly people admitted to six hospitals in New York State between November and April 1989-1992. This and other studies suggest that RSV is likely to be found in ~5% of patients hospitalised with acute respiratory disease, though with molecular diagnostic tests, the number identified is likely to be higher. Previous studies indicate that at least 10% of cardiopulmonary admissions have influenza, but the number of admissions is influenced by the severity of epidemics, which have been mild since 1999/2000. None of these studies were conducted in the United Kingdom, and referral and admission practices may differ between countries. About one-third of all patients who are hospitalised in Northern Europe with community-acquired pneumonia have *S. pneumoniae* infection.

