#### 5 STUDY POPULATION

#### 5.1 Study setting

This study will be done in three hospitals (Leicester Royal Infirmary, Glenfield Hospital, and Leicester General Hospital) that provide acute medical care for the University Hospitals of Leicester (UHL) Trust, Principally in the Medical Assessment Units. The UHL Trust serves a population of approximately 1 million subjects of all ages. The University Hospitals of Leicester NHS Trust is the only facility within the county of Leicestershire providing inpatient emergency medical care to the inhabitants of Leicestershire (population ~ 1 million). The laboratory tests will be carried out in the Molecular Diagnostic Laboratory, and Public Health Laboratory, Leicester Royal Infirmary. The study will carried out during the 36-month period August 1 2005- July 31 2008. Patient enrolment will occur during: September 1 2005 to June 30 2006; September 1 2006 to June 30 2007; & September 1 2007 to June 30 2008.

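### The 10% influenza and 5% RSV prevalences come at least partly from a November–April study but are applied unadjusted from 1 September, so 275 and 138 expected cases are unsupported and should be given as a range

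*Protocol*

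**What the plan says.** Section 7.1 names the Rochester study as its basis and says "we expect that 10% of the 2752 elderly (≥65 years) participants will have influenza A or B". The group sizes follow directly from that: "participants will have influenza A or B. Of the 275, one third (~92) will be allocated to the QuickView near patient influenza immunoassay". For RSV it continues by analogy: "we expect that 5% of the 2752 elderly (≥65 years) participants will have RSV A or B". The synopsis, under sample size, repeats the influenza assumption: "We expect that 10% of the 2752 (elderly) patients will have influenza A or B". From these come 275 influenza and 138 RSV cases (137 in the synopsis), about 92 and 46 per group, and combined groups of 230 (rapid) and 184 (traditional). The same two percentages are reused for the 18–64-year-olds.

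Section 1.2 describes the source study as covering elderly "people admitted to six hospitals in New York State between November and April 1989-1992". Section 1.3 says that influenza viruses circulate nearly every winter, and section 1.4 places RSV outbreaks mostly between November and May.

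The 2752 rests on 242 + 242 + 182 = 666 recruiting days, with each season opening on 1 September. Section 5.1 gives longer windows, for example "September 1 2006 to June 30 2007". Neither section adjusts the prevalences for season.

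**The concern.** A prevalence observed from November to April is an in-season figure. Applied to everyone recruited from 1 September, it treats September and October admissions as if they came at the height of the virus season. Unless something offsets this, the expected number of infected patients is biased upward.

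The infected subgroups matter. In section 7.5.1, time to stopping antibiotics, neuraminidase inhibitor use, time to a single room and the proportion isolated are all restricted to patients with influenza or RSV. Section 7.1 already concedes that these groups are fairly small and pools them to compensate. Sensitivity for each virus is also estimated in the infected patients only, so the precision in section 7.4 depends on the same counts.

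**Working it through.** **Inputs.** From section 7.1 and the synopsis: 666 days; 11.57 elderly admissions a day; factors 5/7, 2/3 and 3/4; prevalences 10% and 5%. From section 1.2: source season November–April. From section 7.4: 80% sensitivity and 20% dropout. Not in the protocol, so assumed: the ratio *r* of off-season to in-season prevalence, varied from 0 to 1, and even admissions over the calendar.

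**The plan's own figures.** 666 × 11.57 × 5/7 × 2/3 × 3/4 = 2752. Then 0.10 × 2752 = 275.2 and 0.05 × 2752 = 137.6. One third of each is 91.7 and 45.9, rounded to 92 and 46. The combined groups are 92 + 92 + 46 = 230 and 92 + 46 + 46 = 184. All reproduce.

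**Share of days outside the source season.** September plus October is 61 days, in three seasons: 3 × 61 = 183, and 183/666 = 27.5%. That leaves 483 days in season (72.5%).

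**Expected cases.** Cases = 2752 × prevalence × (483 + *r* × 183)/666. The rapid group is (2 × influenza + RSV)/3 and the traditional group is (influenza + 2 × RSV)/3. Precision is 2SE = 2 × √(0.8 × 0.2 / (0.8 × cases)).

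| *r* | Influenza | RSV | Rapid | Traditional | 2SE influenza | 2SE RSV |
|---|---|---|---|---|---|---|
| 1 | 275 | 138 | 230 | 184 | 5.4% | 7.6% |
| 0.5 | 237 | 119 | 198 | 158 | 5.8% | 8.2% |
| 0.25 | 218 | 109 | 182 | 146 | 6.1% | 8.6% |
| 0 | 200 | 100 | 166 | 133 | 6.3% | 8.9% |

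At *r* = 0 the average prevalence over the whole calendar is 7.3% for influenza and 3.6% for RSV. To keep 275 and 138 with no September–October cases, the in-season prevalences would have to be 10% × 666/483 = 13.8% and 5% × 666/483 = 6.9%.

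**Pairing in section 7.4.** The section prints 7.6% for a prevalence of 10% and 5.4% for 5%. The formula gives the reverse: 2 × √(0.16/(0.8 × 275)) = 5.4% and 2 × √(0.16/(0.8 × 138)) = 7.6%. This is a separate slip, but any restated precision has to start from the right pairing.

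**The longer windows of section 5.1.** From 1 September to 30 June in three seasons is 910 days, of which November–April is 544. At the same rates, 11.57 × 910 × 5/7 × 2/3 × 3/4 gives about 3760 elderly recruits. With no cases outside November–April, that is 3760 × 0.10 × 544/910 = about 225 influenza and 3760 × 0.05 × 544/910 = about 112 RSV. Counting the 93 May days as RSV season, as section 1.4 suggests, gives 3760 × 0.05 × 637/910 = about 132 RSV. The totals of 275 and 138 are reached at *r* of about one third, since 376 × (544 + 366/3)/910 = 275.

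**The case against.** A reader might infer that 275 and 138 are simply too high. The documents do not support that.

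- Section 1.2 treats the influenza figure as a minimum, and draws it from several studies: they "indicate that at least 10% of cardiopulmonary admissions have influenza, but the number of admissions is influenced by the severity of epidemics". Only one study's months are given. The RSV figure likewise rests on more than that study, and section 7.1 ties RSV to it only by analogy.
- Section 1.2 expects molecular tests to find more RSV. Section 7.3 counts a patient as infected on any positive test, PCR included. Better detection could offset some or all of a dilution of at most 27%.
- Admissions may be weighted to winter, which would shrink the September–October share. Section 1.5 reports multi-week peaks in Leicester pneumonia admissions.

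All of this stands as a reason to treat the low ends as worst cases. None of it rescues the point estimates: section 7.1 uses exactly 10% and 5%, offers no such offset, and never claims in-season levels of 13.8% and 6.9%. Section 1.2 also notes mild epidemics since 1999/2000, which pulls the other way.

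Two further inferences should be resisted. Spreading 2752 over the 910 days of section 5.1 would give about 165 influenza cases (2752 × 0.10 × 544/910), but 2752 is the yield of 666 days, and enrolling in extra months cannot remove cases. Nor does the point undermine the stated power for length of stay and isolation. As written in section 7.4, both are framed on 2752 patients and use neither prevalence. Two of the four prescribing endpoints cover all patients given antibiotics, and one isolation endpoint concerns *S. pneumoniae*. These do not depend on the virus counts either.

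**Conclusion.** The season mismatch is real on the protocol's own text. The arithmetic is correct; the planning assumption behind it is not justified for the enrolment calendar. On the 666-day plan the expected cases, per-group numbers and combined groups are likely optimistic by between 0 and 27%: about 200–275 influenza, 100–138 RSV, 166–230 rapid and 133–184 traditional. The 2SE at 80% sensitivity is 5.4–6.3 points for influenza and 7.6–8.9 for RSV.

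The range assumes that 10% and 5% hold in November–April, that admissions are even over the calendar, and that off-season prevalence lies between zero and the in-season level. Where the truth lies within it cannot be settled from the protocol.

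**What to change.** - In section 7.1 and the synopsis, apply 10% to the share of patients expected in November–April, and 5% to the same share extended to May for RSV. State an assumed lower prevalence for the remaining enrolment months, and restate expected cases, group sizes and combined groups as a range.
- In section 7.4 and the synopsis, give precision at the resulting lower prevalences, starting from the correct pairing (5.4% at 10% and 7.6% at 5%).
- If the 1 September–30 June windows are the intended ones, recompute the number recruited as well (about 3760 elderly at the same rates, with at least about 225 influenza and 112–132 RSV cases) rather than carrying 2752 over.

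The cost is text only, with no change to recruitment or procedures. The downside is that the stated subgroup sizes and precision become less favourable.

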#### 1.8 Diagnostic tests pneumococcal pneumonia

Diagnosis of pneumococcal pneumonia is complicated by the lack of a diagnostic reference standard that is highly sensitive and specific. Despite being the single most important pathogen causing CAP, *S pneumoniae* is undoubtedly underdiagnosed due to limitations of conventional tests. Limitations of Gram stain and culture of sputum include failure to obtain a sputum sample – only a minority of patients are able to produce sputum samples; the overall diagnostic yield of sputum examination is very low (<25%); and isolation of *S pneumoniae* from sputum may represent colonisation. Historically, blood cultures were considered a standard of care for the investigation of patients with CAP. Positive blood culture results are found in <10%

of patients with CAP. The test is rarely useful, as positivity becomes evident no earlier than 24h after obtaining the specimen, and results typically have little influence on therapeutic decisions and outcomes. However, a review of patients with confirmed pneumococcal pneumonia, found that 42% of patients with positive blood culture results had their treatment changed as a result. Since the overall prevalence of  $\beta$ -lactam resistance remains low in the UK, rapid near patient testing for pneumococcal infection could influence therapeutic decisions.

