#### 1. Diagnostic accuracy

Assuming that the average sensitivity/specificity of the tests is 80%[90%] then allowing for a 20% dropout rate, a sample of 2752 (2000 i.e. only 2 winters) elderly patients randomised into the trial would enable the sensitivity/specificity to be estimated to within, i.e. 2SE, 7.6% (8.9%) [5.7% (6.7%)] for a disease prevalence of 10%, and 5.4% (6.3%) [4.0% (4.7%)] for a disease prevalence of 5%.

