#### 7.6 Statistical analysis

All analyses for both process and clinical outcomes will be based on Intention to Treat (ITT) analyses.

Impact of test result on prescribing The time to prescription of `narrow spectrum', `oral antibiotics' or `no antibiotics' between the three groups will be assessed using survival analysis techniques, whilst the use of neuraminidase inhibitors in those with influenza will be assessed using  $\chi^2$  tests, together with 95% CIs. Further analyses to allow for potential differences in patient demographics and baseline clinical characteristics between the three diagnostic test groups, and not allowed by stratification, will make use of cox proportional hazards regression modelling in the case of time to appropriate prescribing and logistic regression techniques in the case of neuraminidase inhibitors.

*Length of hospital stay* Length of hospital stay in the three diagnostic groups will initially be compared using non-parametric methods. Further analyses to allow for potential differences in patient demographics and baseline clinical characteristics between the three diagnostic test groups, and not allowed by stratification, will make use of generalised linear models in order to accommodate any skewness in the data.

*Mortality rates* Mortality rates between the three diagnostic testing groups will be compared by means of a Log-Rank Test and Kaplan-Meier survival curves. Adjustment for potential differences in patient demographics and baseline clinical characteristics between the three diagnostic test groups, and not allowed by stratification, will make use of Cox proportional hazards regression methods.

*Diagnostic accuracy* Sensitivity, specificity, positive predictive value of molecular and near patient diagnostic tests in comparison to traditional laboratory methods will be calculated together with 95% CIs. Heterogeneity in the sensitivity and specificity with respect to patient demographics and baseline clinical characteristics will be explored as secondary analyses using patient defined sub-groups.

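### The RSV sensitivity precision in section 7.4 counts every infected patient, but sensitivity against culture rests on culture-positives, which section 7.1 expects to be scarce

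*Protocol*

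**What the plan says.** Diagnostic accuracy is objective 1 and one of three endpoints for which section 7.4 (and the synopsis, under statistical power) gives a sizing statement. The premise is: "Assuming that the average sensitivity/specificity of the tests is 80%[90%] then allowing for a 20% dropout" rate. The result is a 2SE of "7.6% (8.9%) [5.7% (6.7%)] for a disease prevalence of 10" per cent, with 5.4% (6.3%) [4.0% (4.7%)] for a prevalence of 5%. Figures in round brackets are for 2000 patients and figures in square brackets for 90% accuracy.

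Section 7.1 expects 275 influenza and 138 RSV infections among the 2752 elderly participants. For RSV it adds that the "diagnostic accuracy of the tests will be assessed in all 138 subjects", since identical samples are taken from everyone. The sentence just before it, on the RSV infections allocated to traditional testing, reads "We expect that very few of these will be found" positive by the routine tests.

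On the comparator, objective 1 in section 2.1 names traditional laboratory culture. Section 7.6 says that the accuracy measures of "molecular and near patient diagnostic tests in comparison to traditional laboratory methods will be calculated together with 95% CIs". Section 7.5.3 is broader: traditional and other tests, with serology as an example, plus a discrepant analysis. On pneumococcus, section 1.8 reports "Positive blood culture results are found in <10" per cent of patients with community-acquired pneumonia.

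**The concern.** Sensitivity against a reference is calculated only among patients positive on that reference. If the reference is culture, infections that culture misses do not enter the sensitivity denominator, however many of them there are. Section 7.4 is built on all infections, while objective 1 and section 7.6 describe an analysis restricted to reference-positives. For RSV, two adjacent sentences of section 7.1 pull apart: one expects the routine tests to find hardly any of the infections, the next offers all 138 as the basis for accuracy.

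At stake is whether the trial can say anything useful about how sensitive the molecular RSV test is in this population. A reader of section 7.4 would expect an interval of a few points either side. Against culture, the estimate could rest on a few dozen patients or fewer.

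**Working it through.** **Inputs.** From section 7.4: N = 2752, 20% dropout, sensitivity 80% [90%], criterion 2SE. From section 7.1: prevalence 10% for influenza and 5% for RSV; 664 elderly pneumonias. From section 1.8: blood culture positive in under 10% of community-acquired pneumonia. The protocol gives no culture yield for RSV or influenza, so yields below are assumptions shown as a range.

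**Step 1: reproduce the printed figures.** 2SE = 2 × √(p(1 − p)/n), with n = 2752 × 0.8 × prevalence.
- Prevalence 10%: n = 220.2, so 2SE = 5.4 points at 80% and 4.0 at 90%.
- Prevalence 5%: n = 110.1, so 2SE = 7.6 points at 80% and 5.7 at 90%.

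With n = 160 and 80 (2000 patients) the formula gives 6.3 [4.7] and 8.9 [6.7]. All eight printed values are matched, but with the two prevalence labels exchanged: section 7.4 prints 7.6 beside 10% and 5.4 beside 5%. The exchange is a separate error. What matters here is that the printed values arise with every evaluable infected patient as the denominator.

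**Step 2: RSV against culture.** Denominator = 110.1 × yield.

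| Share of RSV infections found by culture (assumed) | n | 2SE at 80% | 2SE at 90% |
|---|---|---|---|
| 100% | 110 | 7.6 | 5.7 |
| 50% | 55 | 10.8 | 8.1 |
| 25% | 27.5 | 15.3 | 11.4 |
| 10% | 11 | 24.1 | 18.1 |

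Inverting the formula at 80%, a 2SE of 7.6 needs 4 × 0.16/0.076² = 111 reference-positives, in effect all evaluable RSV infections. A 2SE of 5.4, the value printed beside 5%, needs 4 × 0.16/0.054² = 219, about twice as many as there are. Relative to 7.6, the loss is 1/√yield: 1.4, 2.0 and 3.2 times for the three lower rows. In the last row 80% + 24 points exceeds 100%, so the normal approximation is failing and the figure indicates only the order of size.

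**Step 3: influenza.** n = 220.2 × yield gives 5.4 points at 100%, 7.6 at 50% and 10.8 at 25%. The 7.6 printed beside 10% is met if culture finds about half the infections. The 5.4 that belongs to 10% once the labels are corrected would need all of them.

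**Step 4: pneumococcus.** Blood culture alone, elderly pneumonias only: at most 664 × 0.10 × 0.8 = 53 evaluable positives, so 2SE is at least 2 × √(0.16/53.1) = 11.0 points. Adding the 83 younger pneumonias of section 7.1 gives 747 × 0.10 × 0.8 = 59.8 and 10.3 points.

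**Step 5: specificity.** The denominator is the reference-negatives. Even if all infections were removed, 2752 × 0.8 × 0.9 = 1981 remain at 10% prevalence, so 2SE is 1.8 points at 80%. A low culture yield only enlarges this group.

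**The case against.** The strongest reply is that culture alone is not settled as the reference. Section 7.5.3 adds serology and discrepant analysis, section 6.2.12 collects convalescent sera for paired influenza and RSV serology, and section 1.6 says that culture and serology together have served as the gold standard for influenza. Section 7.3 goes further and counts a patient as positive on any one test. Any of these would raise the number of reference-positives.

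This stands as a limit on scope: the shortfall is demonstrated for culture, not for every reference that the protocol mentions. It does not rescue the printed figure. Objective 1 and section 7.6 still name traditional culture or methods. Section 1.4 describes both culture and complement fixation as relatively insensitive for RSV in the elderly, and convalescent serum comes only from survivors. The section 7.3 definition approaches all infections only by counting PCR positivity, which for RSV is the test being evaluated.

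It can also be said that the reference to all 138 subjects means only that accuracy is not confined to one randomised group, and that the remark on scarce positives concerns the roughly 92 infections in the traditionally tested groups. Both readings are fair. But section 6.1.14 provides the same prompt viral culture in all three groups, so the low yield applies to all 138, and step 1 shows that the sizing uses all infections whatever that sentence was meant to convey.

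For pneumococcus the reply largely succeeds. Section 7.4 states no pneumococcal precision, traditional methods here include sputum culture as well as blood culture, and section 7.1 expects further cases among 649 participants with unspecified lower respiratory infections. In the other direction, the under-10% figure is not specific to pneumococcus, so positives for it may be fewer.

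**Conclusion.** The point holds for RSV. Measured against culture, RSV sensitivity cannot attain the stated precision at any yield below 100%: the best case is 7.6 points, and assumed yields of 50%, 25% and 10% give about 11, 15 and 24 points at 80% sensitivity. The protocol's own expectation points to the low end of that range but supplies no number, so the range is illustrative. The underlying defect is that objective 1, section 7.5.3 and section 7.6 do not agree on one reference standard, and the sizing follows none of them explicitly.

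A reader might infer that the precision is out of reach for all three pathogens, or that every sensitivity will be two to four times less precise than planned. The documents do not support either. For influenza no culture yield is given, and about 50% would meet the value printed beside 10%. For pneumococcus there is no stated figure to miss, and the bound of about 11 points applies to blood culture alone in elderly pneumonia. The RSV ratios run from 1.4 to 3.2 over the assumed yields. Specificity is untouched.

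**What to change.** 1. Reconcile objective 1 (section 2.1), section 7.5.3 and section 7.6 into one named reference standard per pathogen, which must not include the test being evaluated.
2. In sections 7.1 and 7.4 item 1, and in the matching synopsis text, replace the all-infections basis with the expected number of reference-positives for that standard. Where the yield is unknown, show 2SE over a range of yields labelled as assumed, rather than one figure.
3. State the precision for specificity separately from that for sensitivity.
4. Label RSV sensitivity against culture alone as descriptive.

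The prevalence labels in section 7.4 item 1 should be corrected in the same edit, since the figures are being restated. No extra patients, samples or tests are needed. The cost is that the printed sensitivity precision becomes less favourable, most of all for RSV.
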